## **5.6 Study Procedures – Assessment of Safety, Plasma Concentration, and Possible Anti-Tumor Efficacy**

*Safety Assessment:* The safety of CPI-613 will be assessed based on:

- physical exams
- vital signs
- clinical pathology

- clinical chemistry
- renal function
- hematology

For physical exams and vital signs, they are to be performed during screening (performed within 2 weeks prior to treatment with CPI-613) and after CPI-613 administration in Cycle 1. Beyond Cycle 1, physical exam and vital signs will be assessed within 5 days of the next cycle doses.

For clinical pathology (i.e., clinical chemistry, renal function, hematology and coagulation), they are to be performed during screening (performed within 2 weeks prior to treatment with CPI-613), and within 24 hrs prior to dosing. Creatinine results within the last 24 hours must be reviewed prior to CPI-613 dosing. For Day 1 of Treatment Cycle 1, pre-dose assessments of clinical pathology are not needed because the pre-enrollment results can be used. Beyond cycle 1, laboratory assessments will be assessed on at least day 1 and 5 of each cycle rather than prior to beginning each cycle.

For left ventricular ejection fraction assessments, they are evaluated during screening and prior to consolidation therapy. Additional assessments can be made at the discretion of the treating physician.

*Anti-Tumor Efficacy – A Secondary Endpoint:* Baseline anti-tumor efficacy (i.e., bone marrow biopsy) will be obtained within 2 weeks prior to the first dose of treatment cycle 1. Follow-up anti-tumor efficacy will be obtained on day 14 of cycle 1. In patients treated with additional treatment cycles beyond Cycle 1, anti-tumor efficacy will be assessed upon count recovery (defined as ANC>1000, freedom from RBC transfusions and platelets>100k) or day 42 from the first day of the cycle whichever comes first. Anti-tumor efficacy assessment will also be based on investigator and institutional routine monitoring of the disease progression of the patients, together with baseline evaluations performed prior to treatment with CPI-613. During maintenance therapy anti-tumor efficacy will be assessed after every 4th cycle.

*Optional Sampling and “Banking” of Blood, Plasma, urine and Bone Marrow Biopsy Samples:* Optional blood samples (5 mL), urine (5-10 ml) as well as bone marrow via biopsy (if deemed appropriate by physician), will be obtained and “banked” for possible testing of biomarkers, predictors of biological responses, toxicity, relationship between genotype and drug responses, etc. These samples will be obtained prior to treatment initiation, as well as prior to and following administration of CPI-613 during salvage Cycle 1. The specific procedures are outlined below.

#### Whole Blood Sample

- One (5 mL) Lavendar Top K EDTA Vacutainer Tube will be used.

- Do not centrifuge or freeze sample.
- Label sample and store at refrigerated temperature (2-8°C).
- Samples will be shipped on ice pack to the address shown at the bottom of this section.

Fresh Bone Marrow Biopsy for Banking of Tumor Cells

- Samples will be collected into a green top lithium heparin tube. Harvested fresh tumor specimens are placed on ice and shipped to the address below. (Note the tumor bank will Ficoll separate mononuclear cells and freeze aliquots in RPMI media containing 10% DMSO.)

Urine Samples

Urine samples will be collected from the first void after the first infusion of CPI-613 in the first induction cycle only. Details of the collection will be recorded on Appendix G.

- Approximately 5-10 ml of urine will be collected in a 15 mL conical tube
- The tube will placed at 4°C until placed into the Tumor Tissue Core Facility (see below)

All optional samples and specimens should be shipped to:

Wake Forest Cancer Center  
Tumor Tissue Core Facility  
Care of [name]  
[name]  
[name]  
[name]

## 5.7 Specifics of Tests Performed During the Study

*ECOG PS:* The ECOG performance status (see Table below) will be used to classify patient's functional impairment. The higher the score, the worse the survival for most serious illnesses including AML.

### ECOG Performance Scale (EPS)

| Score    | Definition   |
|----------|--|
| 0 | Fully active, able to carry on all pre-disease performance without restriction   |
| 1 | Restricted in physically strenuous activity but ambulatory and able to carry out work of a light or sedentary nature, e.g., light house work, office work. |
| 2 | Ambulatory and capable of all self-care but unable to carry out any work activities. Up and about more than 50% of waking hours.                           |
| 3 | Capable of only limited self-care, confined to bed or chair more than 50% of waking hours.   |
| 4 | Completely disabled. Cannot carry on any self-care. Totally confined to bed or chair.  |
| 5 | Dead.  |

CCCWFU 22215

Comprehensive Cancer Center of Wake Forest University

An Open Label Study to Evaluate the Feasibility of CPI-613 Given with High Dose Cytarabine and  
Mitoxantrone in Patients with Relapsed or Refractory Acute Myeloid Leukemia (AML)

**NCT Clinicaltrials.gov:** NCT02484391

*Lab Studies:* Clinical chemistry assessed includes the following parameters.

Renal function will be assessed utilizing the Cockcroft-Gault formula.

|                  |  |
|------------------|--|
| glucose          | uric acid  |
| creatinine       | blood urea nitrogen (BUN)                          |
| total protein    | AST/serum glutamic-oxaloacetic transaminase (SGOT) |
| albumin          | ALT/serum glutamic-pyruvic transaminase (SGPT)     |
| Na +  | alkaline phosphatase (ALP)                         |
| K +   | lactate dehydrogenase (LDH)                        |
| Cl   | total bilirubin                                    |
| Mg               |  |
| Ca +2 |  |
| PO 4  |  |
| CO 2  |  |

Hematology includes:

Complete blood count with differential

Coagulation includes:

|     |                             |
|-----|-----------------------------|
| INR | partial thromboplastin time |
|-----|-----------------------------|

## 5.8 Future Research

Optional blood samples will be collected before and at various times after the 1st dose of CPI-613. Provisions should be made to record and report the actual clock times when samples are drawn. Whenever possible samples should be taken 5 minutes before and at completion of the infusion of CPI-613 on day 1 and at 2, 4 and 6 hours after the completion of the infusion. Blood (5 mL for each sample) should be obtained from an IV catheter that is not used for administration of CPI-613. The blood samples should be collected in 5-mL lavender top collection tubes containing K2- or K3-EDTA anticoagulant. Immediately after blood collection, gently invert tube 3 times to ensure proper mixing of blood and anticoagulant. Blood should then be immediately placed at 4 degrees Celsius. Additionally, several milliliters of urine from the first void following completion of the CPI-613 infusion on day one will be collected in consenting subjects. Once collected 5-10 ml of urine should be placed in a 15 ml conical tube and placed at 4 degrees Celsius until it can be sent to the tumor tissue core facility (see below).

When all samples have been collected, they should be sent to:

Wake Forest Cancer Center  
Tumor Tissue Core Facility  
Care of [name]  
[name]  
[name]  
[name]

Email: [[contact]](mailto:[contact])

### **5.9 Criteria for Removal from Study**

Listed below are criteria for the discontinuation of the study. However, patients who fail to return for the follow-up visits will be contacted and queried as to the reason they have failed to complete the study with special attention to health status.

- A. Patients have the right to withdraw from the study at any time for any reason.
- B. The investigator has the right to withdraw patients from the study according to his/her discretion, if the investigator determines that continued participation is not in the patient's best interest. As an excessive rate of withdrawals can render the study not interpretable, unnecessary withdrawal of patients should be avoided. When a patient discontinues investigational treatment, the investigator should make every effort to contact the patient and to perform a final evaluation. The reason(s) for withdrawal must be recorded. Criteria for terminating subject's participation in the study are listed below:
  - Protocol defined disease progression significantly greater than expected
  - Unacceptable toxicity of the investigational product
  - Patient withdrawal of consent
  - Investigator's discretion
  - Undercurrent illness: a condition, injury, or disease unrelated to the intended disease for which the study is investigating, that renders continuing the treatment unsafe or regular follow-up impossible
  - General or specific changes in the patient's condition that renders the patient ineligible for further investigational treatment
  - Non-compliance with investigational treatment, protocol-required evaluations or follow-up visits
  - Termination of the clinical trial by the sponsor

### **6.0 Dosing Delays/Dose Modifications for CPI-613**

The occurrence of Grade 1 toxicity does not generally require dose modification for subsequent doses for that patient. However, if Grade 2 non-hematologic, non-infectious toxicity develops attributed as at least probably related to CPI-613, treatment can resume only after the Grade 2 toxicity has been reduced to Grade 1 or below, and the dose level for subsequent doses for that patient will be reduced by 25% of the dose at which such Grade 2 toxicity occur. If Grade 3 or 4 non-hematologic, non-infectious toxicity develops, dosing of that patient will be withheld and the patient shall be monitored for recovery from, and reversibility of, such Grade 3 or 4 toxicity. To resume treatment for a patient who has had Grade 3 or 4 toxicity, the Grade 3 or 4 toxicity must be reduced to Grade 1 or below, and the dose level for subsequent doses for that patient will be reduced

to 50% of the dose at which such Grade 3 or 4 toxicity occur. If the reduced dose of CPI-613 results in no toxicity, patients may be dose escalated to the prior dose at the discretion of the treating physician.

Dose adjustments during maintenance therapy will be done as described above with the addition that should patients experience hematologic toxicity  $\geq$  Grade 2 attributed to CPI-613 the next dose of maintenance therapy must be held until the Grade 2 toxicity has been reduced to Grade 1 or below, and the dose level for subsequent doses for that patient will be reduced by 25% of the dose at which such Grade 2 toxicity occurred. If Grade 3 or 4 hematologic toxicity develops, dosing of that patient will be withheld and the patient shall be monitored for recovery from, and reversibility of, such Grade 3 or 4 hematologic toxicity. To resume treatment for a patient who has had Grade 3 or 4 hematologic toxicity, the Grade 3 or 4 hematologic toxicity must be reduced to Grade 1 or below, and the dose level for subsequent doses for that patient will be reduced to 50% of the dose at which such Grade 3 or 4 hematologic toxicity occurred. If the reduced dose of CPI-613 results in no toxicity, patients may be dose escalated to the prior dose at the discretion of the treating physician.

## 7.0 Adverse Events List and Reporting Requirements

Given the severe nature of the disease and treatment modalities associated with this patient population, any adverse event lower than grade 3 during a patient's treatment AE evaluation period will not be part of data analysis or subject to expedited reporting.

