**List of Adverse Events to be Reported:**

- \*Abdominal pain
- \*Creatinine
- \*Diarrhea
- \*Injection site Reaction
- \*Nausea
- \*Vomiting

All adverse events should be reported on the adverse event log and in ORIS regardless of whether they are on this list.

Asterisk (\*) denotes expected Adverse Events.

All SAEs are required to be reported to Rafael Pharmaceuticals via the provided SAE Reporting Form. All completed forms must be sent to [name] at Rafael. The Comprehensive Cancer Center of Wake Forest University will submit any applicable SAEs to the FDA.

SAE reports must be submitted to Rafael by fax to the following address:

Department of Regulatory and Clinical Affairs  
Rafael Pharmaceuticals, Inc.  
[name]  
[name]  
[contact]  
Telefax: [contact]

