### Analysis Plan:

The primary objective of determining the feasibility of administering CPI-613 in combination with high dose cytarabine and mitoxantrone during induction, consolidation and maintenance therapies will be completed by determining the percentage of patients eligible for maintenance therapy who complete at least 3 cycles. If  $\geq 50\%$  of eligible patients complete 3 cycles of maintenance therapy we will consider this regimen feasible for future study. Given an estimated response rate of 50% and a 25% attrition to stem cell transplant, if we enroll 60 patients we should be able to assess feasibility of maintenance in approximately 22 patients. With 22 evaluable patients, a two-sided 95.0% confidence interval using the large sample normal approximation will extend 22% in either direction from the observed value when the expected value is 50%. Within a dose we should be able to estimate feasibility in 7 patients with a 95% confidence interval extending 36% in either direction.

Participants will also be followed and analyzed for secondary outcomes of response rate and overall survival both overall and by dose. Participants will be monitored for survival through routine follow-up visits. Confidence intervals will be calculated around the estimates of the response rate (CR and CRi). Assuming a response rate of 0.5, with 60 participants, we would be able to create 95 percent confidence intervals with a 0.13 margin of error (0.37, 0.63). We will use Kaplan-Meier estimation to analyze overall survival. The frequency of toxicities experienced by the participants will be presented by type and grade in an effort to monitor and report safety of the treatment.

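### The below-grade-3 exclusion in Section 7.0 keeps out of the safety analysis grade 2 events that Section 6.0 treats as dose-modifying, and its scope is not reconciled with Section 10

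*Combined protocol and SAP*

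**What the plan says.** Section 7.0 opens with a grade floor, justified by the severity of the disease and of its treatment: "any adverse event lower than grade 3 during a patient's treatment AE evaluation period will not be part of data analysis". The same sentence lifts expedited reporting for these events. It covers all treatment phases and makes no exception for events that alter dosing.

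Section 6.0 gives grade 2 events consequences. For a non-hematologic, non-infectious grade 2 toxicity judged at least probably related to CPI-613, "treatment can resume only after the Grade 2 toxicity has been reduced to Grade 1 or below". Later doses are then cut by 25%. In maintenance, hematologic toxicity of grade 2 or higher attributed to CPI-613 is added: "the next dose of maintenance therapy must be held until the Grade 2 toxicity has been reduced to Grade 1 or below". A 25% cut applies here too. Where a lowered dose is tolerated, "patients may be dose escalated to the prior dose at the discretion of the treating physician".

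On reporting, the Analysis Plan in Section 10 says: "The frequency of toxicities experienced by the participants will be presented by type and grade". Section 2.2 lists the monitoring of toxicities in induction, consolidation and maintenance as a secondary objective. Neither mentions a minimum grade. On collection, the list under Section 7.1 adds: "All adverse events should be reported on the adverse event log and in ORIS regardless of whether they are on this list".

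**The concern.** The protocol regards an attributed grade 2 toxicity as important enough to interrupt CPI-613 and lower its dose, yet keeps that toxicity out of the analysis. No section plans a table of holds, reductions or their causes. A patient whose maintenance was delayed or reduced for a grade 2 event, and who had no event of grade 3 or higher, would therefore leave no trace in the safety results.

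Two uses of the data suffer. First, feasibility is judged on completion of at least three maintenance cycles, and Section 5.0 lists intolerable side effects among the reasons maintenance ends. A reader of the feasibility result will want to know what lay behind delays, reductions and stopping. Second, Section 1.5 supports the move to lower doses partly by reduced toxicity. Under Section 5.3, the 500 mg/m² cohort stays at that dose in maintenance while the 1,500 mg/m² cohort receives 2,500 mg/m². Grade 2 differences between cohorts would not be visible.

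The stated reason for the floor also fits maintenance less well, because CPI-613 is given there without cytarabine or mitoxantrone.

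**Working it through.** The point rests mainly on text, so the provisions are set side by side first.

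| Provision | Grade 2 events attributed to CPI-613 |
|---|---|
| Section 6.0, all phases | Hold and 25% reduction if non-hematologic, non-infectious and at least probably related |
| Section 6.0, maintenance | The same consequences for hematologic toxicity attributed to CPI-613 |
| Section 7.0 | Excluded from data analysis |
| Section 7.1 list | Logged whether or not listed; silent on grade |
| Section 2.2 and Section 10 | Monitored, and presented by type and grade; no floor stated |

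**Step 1: is there a gap?** Section 6.0 needs these events to be graded and attributed before a dosing decision can be made. Section 7.0 then removes them from analysis without exception. The cause of a required dose change can therefore be missing from every planned table.

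**Step 2: does Section 10 close it?** Not clearly. One analyst could tabulate grades 1 to 5 from Section 10; another could apply Section 7.0 and tabulate grades 3 to 5. Both could claim to follow the plan.

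**Step 3: is the primary estimate affected?** No. Sections 2.1 and 10 count patients who complete at least three cycles. Adverse event grades do not enter the calculation, and no section counts a hold or a reduced dose as non-completion.

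**Step 4: how many patients could be involved?** Section 10 assumes 60 enrolled, a 50% response rate and 25% attrition to transplant:

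60 × 0.50 × 0.75 = 22.5, which reproduces the plan's approximate 22.

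The documents give no rate for grade 2 events that modify dosing. Taking p as an assumption, patients affected = 22 × p:

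- p = 10%: 22 × 0.10 = 2.2
- p = 30%: 22 × 0.30 = 6.6
- p = 50%: 22 × 0.50 = 11.0

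This treats all 22 as starting maintenance. It counts everyone with such a modification, including any who also have an event of grade 3 or higher and so would appear in the tables through that event.

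**Step 5: why an explanation is worth having at this size.** With 22 patients, one patient is 1/22 = 4.5 percentage points. Eleven completers give 11/22 = 50.0%, which meets the 50% criterion; ten give 10/22 = 45.5%, which does not.

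**Step 6: by dose.** For a cohort of 20, 20 × 0.50 × 0.75 = 7.5, against the plan's 7. The normal-approximation half-width at 50% is 1.96 × √(0.25/7.5) = 0.358, in line with the plan's stated 36%. Grade 2 comparisons between cohorts can only be descriptive.

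**The case against.** A grade 3 floor is a deliberate choice with a stated reason, and in relapsed or refractory AML under intensive chemotherapy it keeps low-grade noise out of the tables. That stands as an argument against requiring every grade to be tabulated. It does not reach the narrower set of events that lead to a change in CPI-613 dosing.

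A reader might infer that the omitted events drive the primary endpoint, or that this is a tolerability endpoint. The documents do not support this. The endpoint is feasibility, measured by cycles completed. A patient may resume after a hold, continue on a reduced dose and be re-escalated, and progression or transplant can also end maintenance. Grade 2 toxicity can affect completion, but nothing shows that it determines it.

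A reader might also infer that Sections 7.0 and 10 flatly contradict each other. They need not: a table of grades 3, 4 and 5 is still by type and grade. The fair description is unreconciled scope.

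Three further objections have some force:

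- The logging instruction in Section 7.1 concerns events not on the list and is silent on grade. That grade 2 events are logged is the likelier reading, but it is not certain.
- The attribution scale in Section 7.1 refers to the study treatment as a whole, which is three drugs in induction and consolidation, so a table defined by attribution to CPI-613 might lack a data field. A table defined by the dosing action avoids most of this.
- Section 5.9 requires withdrawal reasons to be recorded. This captures discontinuations, though no table of reasons is planned, and it does not cover holds or reductions.

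Finally, the by-dose commitment in Section 10 attaches to response and survival, not toxicity, and about 7 maintenance patients per dose make contrasts imprecise. Both points limit what a by-dose display can show; neither is a reason to omit it.

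**Conclusion.** The point holds as a gap in safety reporting and not as a flaw in the primary analysis. As written, the safety tables leave out grade 2 events that Section 6.0 treats as requiring a hold and a 25% reduction, and the scope of Sections 7.0 and 10 needs to be reconciled. The feasibility estimate does not change. What is lost is an account of why maintenance was delayed, reduced or stopped, and sight of grade 2 differences between cohorts.

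The number affected cannot be taken from the documents. The figure of about 2 to 11 of 22 rests on an assumed rate of 10% to 50% and on all 22 patients starting maintenance; it is illustrative, and the conclusion does not depend on it. This is a cheap improvement.

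**What to change.** 1. **Section 7.0.** Exempt from the below-grade-3 analysis exclusion any adverse event, of any grade, that leads to a CPI-613 hold, reduction or discontinuation. The exclusion of other low-grade events, and of all events below grade 3 from expedited reporting, can stay.
2. **Section 10.** Add a table of these events by type, grade, treatment phase and dose cohort. State that the general toxicity tables follow the Section 7.0 floor, so that the two sections agree.
3. **Section 7.1.** Make explicit that the logging instruction covers these events regardless of grade.

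The cost is a few sentences and slightly longer safety tables. The grading and attribution are already needed for the Section 6.0 dosing decision. The adverse event log is not reproduced in the appendices, so the sponsor should confirm that it records the action taken with CPI-613 and add that item if it does not. Tabulating all grades throughout is optional. The dosing rules are untouched.

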### 7.1 Adverse Event Characteristics

- **CTCAE term (AE description) and grade:** The CTEP Active Version of the NCI Common Terminology Criteria for Adverse Events (CTCAE 4.0) will be utilized for AE reporting. The CTEP Active Version of the CTCAE is identified and located on the CTEP website at [http://ctep.cancer.gov/protocolDevelopment/electronic\\_applications/ctc.htm](http://ctep.cancer.gov/protocolDevelopment/electronic_applications/ctc.htm). All appropriate treatment areas should have access to a copy of the CTEP Active Version of CTCAE.
- **‘Expectedness’:** AEs can be ‘Unexpected’ or ‘Expected’ (see Section 7.1 above) for expedited reporting purposes only.
- **Attribution** of the AE:
  - Definite – The AE is *clearly related* to the study treatment.
  - Probable – The AE is *likely related* to the study treatment.
  - Possible – The AE *may be related* to the study treatment.
  - Unlikely – The AE is *doubtfully related* to the study treatment.
  - Unrelated – The AE is *clearly NOT related* to the study treatment.

CCCWFU 22215

Comprehensive Cancer Center of Wake Forest University

An Open Label Study to Evaluate the Feasibility of CPI-613 Given with High Dose Cytarabine and  
Mitoxantrone in Patients with Relapsed or Refractory Acute Myeloid Leukemia (AML)

**NCT Clinicaltrials.gov:** NCT02484391

